## I. INTRODUCTION & RATIONALE

Contact lens (CL) discomfort affects most CL wearers with discomfort consistently topping the reasons why established CL wearers drop out of CLs. In fact, studies have consistently found that the frequency of CL dropout is around 20% with this dropout frequency staying relatively stable over the past 20 plus years. This static frequency of CL dropout is surprising since there have been a number of dramatic soft CL innovations during this time frame (e.g., widely available daily disposable CLs, silicone hydrogel CL materials with high oxygen transmissibility, new CL surface coatings).

Another common issue that CL wearers frequently face is that their discomfort symptoms increase towards the end of the wear day. This burdensome discomfort can unfortunately cause patients to remove their CLs before their desired wear time. While comfortable wear times vary from patient to patient, Terry et al. has suggested that patients should be able to comfortably wear their CLs for at least 12 hours per day for at least 6 days per week. Nevertheless, the literature currently lacks sufficient data to comment fully on the full day wear experience, which for many patients may be 16 or more hours per day, especially if they have demanding careers. One CL that has the potential to allow for all day comfort is the Total30 Sphere CLs, which is a new water gradient, monthly CL aimed at delivering all day comfort and visual performance. Therefore, the purpose of this study is to map comfort over the full wear day in established, asymptomatic, soft CL wearers who are refit in Total30 Sphere CLs. These data are not only important for judging the performance of Total30 Sphere CLs, but they will provide some of the first insights into the full day CL wearing experience over one month.

## II. SPECIFIC AIM

We plan to accomplish our goals by pursuing the following specific aim and testing the associated hypothesis:

**Aim 1: Determine if Total30 Sphere CLs provide a comfortable wearing experience all day.**

Hypothesis 1: Patients who are refit in Total30 Sphere CLs will have a comfortable wearing experience after 16 hours as based on visual analog scale (VAS) scores.

## III. STUDY DESIGN

### Subjects

This one-month, three-visit study will be conducted at the University of Alabama at Birmingham (Birmingham, AL, USA). Subjects will be recruited via clinic records, email, and fliers. Subjects will be screened prior to the study visit with an IRB approved phone screening survey. Adult, 18- to 45-year-old, CL wearers who have 20/20 visual acuity or better and who are minimally symptomatic will be recruited (Contact Lens Dry Eye Questionnaire [CLDEQ]-8  $\leq 10$ ). Subjects will be required to be able to wear Total30 Sphere CLs, and they will be required to have a smart phone with text messaging capabilities to be able to answer electronic survey questions. Subjects will be required to have astigmatism better than or equal to -0.50 D in each eye, and they will be required to have regularly worn 2 week or monthly CLs within the past 6 months and be a current CL wearer. Subjects will be required to provide a glasses prescription that is less than 3 years old. Subjects will be required to be willing to start wearing their CLs between 6:00 AM and 8:00 AM and wear their CLs until 11:00 PM each day text messaging data is collected. Subjects will be excluded if they are current or past hard CL wearers, have known systemic health conditions that are thought to alter tear film physiology, have a history of viral eye disease, have a history of ocular surgery, have a history of severe ocular trauma, have active ocular infection or inflammation, are currently using isotretinoin-derivatives or ocular medications, are currently using rewetting drops or artificial tears, or if they are pregnant or breast feeding.

### Sample Size

This will be a pilot study to understand CL comfort throughout the day in monthly soft CL wearers. We estimate that 48 subjects will be enough to gain a general understanding of ocular comfort across the entire day based upon past research (40 subjects + 8 subjects to account for attrition and missing data). An additional 10 subjects are being requested to account for screen fails; however, recruitment will stop when 48 subjects fully qualify for this study (max of 58 subjects).

## Surveys and Clinical Tests

### Visit 1: Baseline

**1. Subject History, Eligibility, Informed Consent:** Subjects will be asked to repeat the IRB approved phone screening survey at the study visit to verify that they are still eligible for the study. All subjects will be screened with the CLDEQ-8 questionnaire regarding their habitual CLs over the past two weeks to verify that they are asymptomatic CL wearers. While subjects will be asked to report to the visit without their CLs, they will be asked to complete the CLDEQ-8 as if they are wearing their habitual CLs. All relevant patient demographics will be collected via a questionnaire developed by the investigators. Non-eligible subjects will be dismissed at this time or rescheduled depending upon the reason for ineligibility. Eligible subjects will be enrolled, consented, and requested to sign a privacy document.

**2. Visual Acuity with Spectacles:** Visual acuity will be measured with a Bailey-Lovie high-contrast chart.

**3. Manifest Refraction:** The investigator will determine the subject's refractive error with a phoropter, and binocular balance will be performed if best-corrected visual acuity is equal in between eyes.

**4. Slit-Lamp Biomicroscopy:** The investigator will use a slit-lamp biomicroscope to document normal and/or remarkable findings of the anterior eye structures: eyelashes (blepharitis), eyelids, conjunctiva, and cornea.

**5. CL Fitting:** Subject will be fit in Total30 Sphere CLs. The CLs will be evaluated for centration, movement, coverage, and CL power adjustments will only be made if they improve Snellen visual acuity. Subjects will be given a 1-month supply of CLEAR CARE® CL solution. Subjects will be educated on how to use CLEAR CARE®.

**6. Subject Compliance & Daily Comfort:** All subjects will be encouraged to wear their CLs for at least 16 hours per day and to start wearing their CLs between 6:00 AM and 8:00 AM on days that they will be completing text messaging surveys. Subjects will be educated that they will be required to complete Qualtrics surveys on their phone. Subjects will be asked to complete a test survey before they leave the first study visit to make sure that their system is compatible with their phone. These surveys will ask subjects about their eye comfort with a visual analog scale (slider scale with 0 as neutral comfort, -50 extremely uncomfortable, and +50 extremely comfortable) at before CL application, directly after CL application, and at 8 hours, 10 hours, 12 hours, 14 hours, and 16 hours post lens application on the first 5 days. This same system will be used to monitor how many hours they wear their CLs each day. Subjects will finally be asked to complete these surveys on day 14 and 1 day prior to their 1-month visit (1 month) to understand comfort over the life of the CLs. Subjects will be called the day before the day 14 and 1-month surveys to remind them about these surveys. Subjects will be allowed to schedule their day 14 and 1-month surveys within 3 days of these time points to allow for better compliance.

### Visit 2: 1 Week

**1. Visual Acuity with CLs:** Visual acuity will be measured with a Bailey-Lovie high-contrast chart.

**2. Slit-Lamp Biomicroscopy:** The investigator will use a slit-lamp biomicroscope to document normal and/or remarkable findings of the anterior eye structures: eyelashes (blepharitis), eyelids, conjunctiva, and cornea.

**3. CL Evaluation:** The CLs will be evaluated for centration, movement, and coverage, and lens power adjustments will only be made if they improve Snellen visual acuity. If a refractive error adjustment of more than 0.25 D is made, the patient will be given a new set of lenses and be required to repeat the 1-week visit.

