### Visit 3: 1 Month

**1. Visual Acuity with CLs:** Visual acuity will be measured with a Bailey-Lovie high-contrast chart.

**2. Slit-Lamp Biomicroscopy:** The investigator will use a slit-lamp biomicroscope to document normal and/or remarkable findings of the anterior eye structures: eyelashes (blepharitis), eyelids, conjunctiva, and cornea.

**3. CL Evaluation:** The CLs will be evaluated for centration, movement, and coverage, and lens power adjustments will only be made if they improve Snellen visual acuity. If interested, the patient will be given a prescription for the CLs upon request.

**4. Study Completion:** The subject will be compensated for their time, and they will be released from the study.

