## Data Analysis

All data will be analyzed with Stata/IC 15 (StataCorp LLC; TX, USA). VAS comfort scores will serve as the primary endpoint and be reported as percent of patients who are comfortable at each timepoint. Comfort comparisons across visits or across the wear day will serve as exploratory endpoints, and these outcomes will be measured with paired t-tests or ANOVA.

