## V. Publication Plans

An abstract describing comfort across the wear day will be submitted to Academy 2022 San Diego (main outcome), and an abstract will be submitted to Heart of America Eye Congress describing how comfort changes over the wear month. A manuscript on the same topics will be submitted to *Contact Lens & Anterior Eye* after the Academy 2022 San Diego abstract is submitted because the Academy requires that abstract materials have not been presented/submitted elsewhere.

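### Do lens replacement at the 1-week visit and the 3-day survey allowance leave the day-14 and 1-month comfort surveys mistimed?

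*Combined protocol and SAP*

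**What the plan says.** Visit 1: Baseline, item 6, places comfort surveys at set times of the wear day, up to "16 hours post lens application on the first 5 days". The same surveys are repeated "on day 14 and 1 day prior to their 1-month visit (1 month) to understand comfort over the life of the CLs". On flexibility it adds: "Subjects will be allowed to schedule their day 14 and 1-month surveys within 3 days of these time points". Staff telephone each subject the day before the day-14 and 1-month surveys.

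Visit 2: 1 Week, item 3, covers a power adjustment of more than 0.25 D: "the patient will be given a new set of lenses and be required to repeat the 1-week visit". It mentions no survey.

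Visit 3: 1 Month, item 4, closes participation: subjects are paid and "they will be released from the study". The Subjects section gives the nominal course: "This one-month, three-visit study will be conducted".

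Data Analysis makes the comfort score the primary endpoint, to "be reported as percent of patients who are comfortable at each timepoint", and treats comparisons across visits or across the wear day as exploratory. Publication Plans calls comfort across the wear day the main outcome and plans a separate abstract "describing how comfort changes over the wear month".

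**The concern.** The later surveys are meant to show how comfort changes as a pair of lenses ages, so day 14 and 1 month stand for lens age. A subject who gets a new pair at Visit 2 breaks that link unless the clock restarts, and the plan does not say whether it does. Without a restart, that subject's first-5-day scores describe a discarded pair and the later scores describe a younger one. The day-14 and 1-month percentages, which fall under the primary endpoint, would then mix lens ages under one label. So would the wear-month comparison.

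The second worry is the allowance. The 1-month survey is set for the day before Visit 3, and 3 days either way extends beyond the visit at which the subject leaves the study.

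**Working it through.** The plan has no figure of its own to reproduce here, so the check is day arithmetic.

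**Inputs.** From the documents: surveys on days 1 to 5, day 14 and Visit 3 minus 1 day; an allowance of 3 days; 40 subjects after attrition (Sample Size). Assumed, because the documents give no exact days: replacement on day R = 7 (range 5 to 10) and Visit 3 on day V = 28 to 31. The replaced fraction f is not given.

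**1. Lens age if the clock does not restart** (survey day minus R, with R = 7).
- Day-14 survey: 14 − 7 = 7 days. With the allowance, 11 − 7 = 4 to 17 − 7 = 10 days.
- 1-month survey, nominal day V − 1 = 27 to 30: lens age 20 to 23 days.
- Over R = 5 to 10 and V = 28 to 31, nominal ages are 4 to 9 days and 17 to 25 days.

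**2. Effect on the wear-month comparison.** Assume comfort changes linearly with lens age. A replaced subject falls short by 7 days of change, so the mean change shrinks by these fractions:
- day 1 to day 14: 7/(14 − 1) = 0.538, times f;
- day 1 to 1 month: 7/(30 − 1) = 0.241 to 7/(27 − 1) = 0.269, times f.

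| f (of 40) | Day 1 to day 14 | Day 1 to 1 month |
|---|---|---|
| 2.5% (1) | 1.3% | 0.6–0.7% |
| 5% (2) | 2.7% | 1.2–1.3% |
| 10% (4) | 5.4% | 2.4–2.7% |
| 20% (8) | 10.8% | 4.8–5.4% |

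These are percentages of the change itself, not points on the comfort scale. With R = 10 and f = 5%, the day-14 figure rises to (10/13) × 5% = 3.8%.

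**3. Effect on percent comfortable.** Each subject carries 1/40 = 2.5 points. That is a ceiling, reached only if a younger lens changes whether the subject counts as comfortable.

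**4. Which rows are plausible.** Replacement needs a change above 0.25 D at Visit 2, and adjustments are made only if they improve acuity. Every subject has by then met the 20/20 and 0.50 D astigmatism limits and had a manifest refraction and a fitting with power adjustment at Visit 1. The upper rows would need many of those fittings to be revised within a week. The documents support no such expectation, though they do not rule it out.

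**5. If the clock does restart** (R = 7, V = 30). The day-14 survey moves to day 14 + 7 = 21, the 1-month survey to 29 + 7 = 36 and Visit 3 to 30 + 7 = 37. Lens ages then match their labels.

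**6. The allowance.** Around V − 1 it runs from V − 4 to V + 2. Of 7 permitted days, one is the visit day and two follow it, whatever V is. But the survey is defined as the day before the visit, so one that follows the visit contradicts its own definition. The two can simply be booked together.

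**7. Would regrouping surveys by actual lens age, without a restart, be better?** With R = 7, the replaced subject's day-14 survey falls at 4 to 10 days and cannot enter the 11-to-17-day window. The 1-month survey falls at V − 11 to V − 5 days, against V − 4 to V + 2 for other subjects, so those ranges do not meet either. If days 1 to 5 on the discarded pair are also set aside, the subject has no value at either planned point and no early value to pair with.

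**The case for a change.** The best argument for a change is that staff must choose a rule the plan does not give, and could choose differently from one subject to the next. A restart is also not free: day 37 sits awkwardly with a one-month, three-visit description and with the 1-month supply of lens solution given at Visit 1. Stating which dispensing date starts the clock, and that the last survey precedes Visit 3, would take two sentences.

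The silence is conceded, and so is the loose wording of the allowance. The rest weighs less. The repeated 1-week visit already makes a fourth visit, so the Subjects section describes the usual course and does not bar a longer one. Staff already book and telephone each subject around these surveys, so a survey set after the final visit would be noticed. The date of a second pair is the date of the visit at which it was given, so lens age can be recovered at analysis. The plan also accepts approximate lens age for everyone, since the day-14 window alone spans 11 to 17 days. Nor does a repeat visit near day 14 disturb a survey answered by phone.

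**Conclusion.** No change to the plan follows. This is unwritten scheduling detail that site staff would fill sensibly: a week on the new lenses before the repeated visit implies a restarted clock, and the last survey belongs with the visit that defines it. If the clock were left running, the loss would be 0.6% to 2.7% of the wear-month change with 1 or 2 of 40 subjects replaced, and at most 2.5 points per replaced subject in any percent comfortable. The hypothesis about comfort after 16 hours is barely affected, because it concerns hours within a day.

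This rests on replacement near day 7, a linear trend with lens age and few replacements. At 8 of 40 the day-14 change would shrink by 10.8%, so the conclusion would weaken if replacements proved common. Regrouping surveys by lens age without a restart would cost the replaced subjects their planned timepoints, so it offers no clear gain.

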### Visit 3: 1 Month

**1. Visual Acuity with CLs:** Visual acuity will be measured with a Bailey-Lovie high-contrast chart.

**2. Slit-Lamp Biomicroscopy:** The investigator will use a slit-lamp biomicroscope to document normal and/or remarkable findings of the anterior eye structures: eyelashes (blepharitis), eyelids, conjunctiva, and cornea.

**3. CL Evaluation:** The CLs will be evaluated for centration, movement, and coverage, and lens power adjustments will only be made if they improve Snellen visual acuity. If interested, the patient will be given a prescription for the CLs upon request.

**4. Study Completion:** The subject will be compensated for their time, and they will be released from the study.

## Data Analysis

All data will be analyzed with Stata/IC 15 (StataCorp LLC; TX, USA). VAS comfort scores will serve as the primary endpoint and be reported as percent of patients who are comfortable at each timepoint. Comfort comparisons across visits or across the wear day will serve as exploratory endpoints, and these outcomes will be measured with paired t-tests or ANOVA.

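### The primary comfort percentage does not say whether it covers all fitted subjects or only those still wearing lenses, and nothing keeps bare-eye answers out of the 16-hour figure

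*Combined protocol and SAP*

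**What the plan says.** The Data Analysis section is the whole analysis plan. On the primary result it says that "VAS comfort scores will serve as the primary endpoint and be reported as percent of patients who are comfortable at each timepoint". It names no denominator and gives no rule for a survey that falls due after the lenses are out.

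Hypothesis 1 (Specific Aim) is that refitted patients "will have a comfortable wearing experience after 16 hours as based on visual analog scale (VAS) scores".

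The survey is described under Visit 1, item 6: "These surveys will ask subjects about their eye comfort with a visual analog scale", given "at before CL application, directly after CL application, and at 8 hours, 10 hours, 12 hours, 14 hours, and 16 hours post lens application". It is used on the first 5 days, on day 14 and just before the 1-month visit, which makes 5 + 1 + 1 = 7 survey days. The same item says that "All subjects will be encouraged to wear their CLs for at least 16 hours per day" and that daily wear hours are tracked through the same system. Neither a lens-in or lens-out question nor a reason for removal is listed.

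The entry criteria (Study Design, Subjects) require willingness to "start wearing their CLs between 6:00 AM and 8:00 AM and wear their CLs until 11:00 PM each day text messaging data is collected".

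The Introduction says of contact lens wearers in general: "This burdensome discomfort can unfortunately cause patients to remove their CLs before their desired wear time". The Sample Size section allows for "40 subjects + 8 subjects to account for attrition and missing data" but does not say how missing data are handled.

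**The concern.** The protocol itself names early removal as a consequence of discomfort, so a subject whose lenses are out late in the day may be out because of the very outcome being measured. A percentage among those still wearing and a percentage among all fitted subjects then answer different questions, and the plan does not choose between them.

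The survey wording adds a second problem. It asks about the eye, not the lens, and it is also given before application, so it can be answered without lenses. Nothing in the document keeps such an answer out of the 16-hour percentage, although Hypothesis 1 concerns the wearing experience.

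At stake is the main reported number and what it may be called. A statement that 90% were comfortable at 16 hours means one thing for everyone fitted and another for those who kept the lenses in. If the choice is left open, it can be made after the results are seen.

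**Working it through.** **1. Sample size.** 40 + 8 = 48, and 48 + 10 for screen failures = 58. The plan's figures reproduce. The largest all-fitted base is therefore 48.

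**2. Who can be in lenses at each survey.** Inputs: start time and 11:00 PM end from the entry criteria; survey hours from Visit 1, item 6.

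| Start | Wear to 11:00 PM | 14-hour survey due | 16-hour survey due |
|---|---|---|---|
| 6:00 AM | 17 h | 8:00 PM | 10:00 PM |
| 7:00 AM | 16 h | 9:00 PM | 11:00 PM |
| 8:00 AM | 15 h | 10:00 PM | midnight |

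A subject who follows the entry criteria is in lenses at every post-application survey through 14 hours. At 16 hours, one who starts after 7:00 AM and removes at 11:00 PM is not. The gap therefore falls mainly on the 16-hour figure, and at other hours on anyone who removes early.

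**3. Size if the target is all fitted subjects.** Assumptions, since the documents give neither rate: n = 48, share of wearers comfortable p = 0.90, and d subjects who removed for discomfort and are counted as not comfortable.

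- Target: (48 − d) × 0.90 / 48
- Removers dropped: reported 0.90, so the overstatement is 0.90 × d / 48
- Removers answer bare-eyed and a share c of them report comfort: the overstatement is c × d / 48

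| d | Target | Overstated if dropped | Overstated if bare-eyed, c = 0.5 | Overstated if bare-eyed, c = 1 |
|---|---|---|---|---|
| 0 | 90.0% | 0 | 0 | 0 |
| 2 | 86.25% | 3.75 points | 2.1 | 4.2 |
| 4 | 82.5% | 7.5 points | 4.2 | 8.3 |
| 8 | 75.0% | 15 points | 8.3 | 16.7 |

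If all bare-eyed removers still report discomfort (c = 0), nothing is overstated. With d = 8, dropping removers gives 0.80 × 8 / 48 = 13.3 points at p = 0.80 and 0.95 × 8 / 48 = 15.8 points at p = 0.95. On a base of 40 instead of 48, the dropped column becomes 4.5, 9 and 18 points.

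**4. Size if the target is comfort while wearing.** Dropping removers gives the right answer, 90%. Bare-eye scores still shift it, by d × (c − 0.90) / 48. With c = 1 this is +0.4, +0.8 and +1.7 points for d = 2, 4 and 8; with c = 0 it is −3.75, −7.5 and −15 points. The direction depends on what removers report.

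**5. What recorded wear hours can settle.** They can show who removed before a survey hour, but not whether the reason was discomfort or the 11:00 PM end. If m subjects have no usable in-lens score and an unknown reason, the all-fitted percentage is known only to within m / 48: 4.2, 8.3 or 16.7 points for m = 2, 4 or 8.

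**The case against.** The strongest reply is that overstatement presupposes a target that the protocol never sets. Its stated purpose is to map comfort across the wear day, and the hypothesis speaks of a wearing experience. Both can be read as comfort while wearing, and then leaving removers out is correct. This stands: a reader might infer from the gap that 16-hour comfort will be overstated, but the documents support that only for a target that counts discomfort removal as not comfortable.

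It can also be said that wear to 11:00 PM is an entry condition, that the enrolled wearers are minimally symptomatic (CLDEQ-8 of 10 or less), and that no removal rate is given. These points stand too. They limit the problem through 14 hours and may make it small, and 8 discomfort removers is an illustration only.

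A reader might infer that the two wear instructions contradict each other. They can both be met, because the entry criteria do not forbid wear past 11:00 PM; but a later starter can also meet the entry criteria alone with lenses out at 16 hours. Nor do the documents show that bare-eye answers will be given: the survey items and any branching are only summarised. What can be said is that no stated rule excludes them.

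Reading percent of patients as all patients does not close the gap, because it leaves lens-out answers unresolved. The test survey, reminder calls and 3-day scheduling allowance reduce missed surveys but do not say how lens-out answers are counted.

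**Conclusion.** The primary percentage is undefined in two respects: whom it describes, and whether a score given without lenses counts. Both matter most at 16 hours, the hour that Hypothesis 1 uses and the only survey hour at which a subject who keeps to the entry criteria may already be out of lenses.

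The direction is conditional and the size unknown. On 48 subjects with 90% of wearers comfortable, both assumed as the base and rate, dropping 2, 4 or 8 discomfort removers would overstate all-fitted comfort by 3.75, 7.5 or 15 points. If nobody removes for discomfort there is no such overstatement, though 11:00 PM removals would still leave later starters without an in-lens score.

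It should be fixed, but at the low end of that grade, because this is a single-group pilot with no success threshold. It is more than wording: no listed item records lens status at each survey or the reason for removal, so the analyst could not fully repair it afterwards.

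**What to change.** Before the first survey is sent:

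1. Reconcile the entry criteria with Visit 1, item 6, so that it is clear which subjects can give an in-lens score at 16 hours.
2. Add an item to the existing survey: lenses in or out and, if out, the time and reason of removal.
3. State that scores given with lenses out do not count as in-lens comfort. The score before application is bare-eye by design and should be labelled so.
4. At each hour and survey day, report two labelled percentages with counts: among all subjects dispensed study lenses, with removal or discontinuation for discomfort counted as not comfortable; and among those still wearing. Name in advance which is primary.
5. Report how many subjects removed for other reasons and how many skipped the survey. Give simple bounds on the all-dispensed percentage, counting all of these first as not comfortable and then as comfortable. Multiple imputation is not needed for a descriptive pilot percentage.

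The cost is analysis wording, a short addition to an electronic survey already in use, and the reconciliation of two sections. No extra visits or subjects are needed. The drawbacks are slight extra subject burden, self-reported reasons for removal, and possibly a less favourable percentage.

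### The plan promises to test comfort after 16 hours, but names no day, summary or interval for that result, and its wear window lets scores given after lens removal into it

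*Combined protocol and SAP*

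**What the plan says.** The Specific Aim section describes "pursuing the following specific aim and testing the associated hypothesis". Hypothesis 1, under Aim 1, is that refitted patients "will have a comfortable wearing experience after 16 hours as based on visual analog scale (VAS) scores".

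The Data Analysis section gives the whole primary analysis in one sentence: "VAS comfort scores will serve as the primary endpoint and be reported as percent of patients who are comfortable at each timepoint". It then assigns paired t-tests or ANOVA to comparisons across visits or across the day, which it labels exploratory.

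Visit 1, item 6 describes the measurement. The scale is a "slider scale with 0 as neutral comfort, -50 extremely uncomfortable, and +50 extremely comfortable". Surveys are sent "at before CL application, directly after CL application, and at 8 hours, 10 hours, 12 hours, 14 hours, and 16 hours post lens application" on each of the first five days, and subjects also "complete these surveys on day 14 and 1 day prior to their 1-month visit". Subjects are "encouraged to wear their CLs for at least 16 hours per day", and on wear time the plan adds: "This same system will be used to monitor how many hours they wear their CLs each day". No section says how the wear-hours data enter the analysis.

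The Subjects section requires willingness, on survey days, to insert lenses from 6:00 to 8:00 AM and keep them in to 11:00 PM. Sample Size calls the study a pilot and sets 40 subjects plus 8 for attrition and missing data.

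**The concern.** There are two problems.

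First, the promised test has no matching analysis. The percent comfortable at 16 hours will be reported, because 16 hours is one of the timepoints. But it will be reported once per survey day, without an interval, and nothing says which figure, or what summary of them, answers Hypothesis 1. The only tests named ask whether comfort changes between times or visits. They do not ask whether subjects are comfortable at 16 hours. If the day is chosen after the data are seen, the choice can favour the lens.

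Second, the 16-hour figure may not describe lens wear for everyone. A subject can meet the wear window in Subjects with lenses removed before the 16-hour survey arrives. That subject's score, given without lenses, would still enter the primary percentage as wearing comfort. This affects exactly the timepoint that the hypothesis names.

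**Working it through.** **1. The plan's own figures.** Sample Size: 40 + 8 = 48 qualified subjects, and 48 + 10 for screen failures = 58. Both sums check. No expected percentage or precision target is given for the base of 40, so there is nothing further to reproduce.

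**2. How many figures there are.** Visit 1, item 6 gives 7 surveys a day on 5 + 1 + 1 = 7 days.
- At 16 hours: 1 × 7 = 7 percentages.
- All timepoints crossed with all days: 7 × 7 = 49 at most, or 49 − 7 = 42 without the scores taken before lens insertion.

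The 7 figures at 16 hours are the ones that matter for Hypothesis 1.

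**3. Clock time of the 16-hour survey.** Start times and the 11:00 PM end come from Subjects; the 16-hour survey comes from Visit 1, item 6.

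| Start | Hours to 11:00 PM | 16-hour survey falls at |
|---|---|---|
| 6:00 AM | 17 | 10:00 PM |
| 7:00 AM | 16 | 11:00 PM |
| 8:00 AM | 15 | midnight |

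Any start after 7:00 AM puts the survey after 11:00 PM. If 25%, 50% or 75% of 40 subjects start after 7:00 AM (assumed; 50% is an even spread), 10, 20 or 30 surveys on a given day fall after 11:00 PM. The documents do not show how many of these would be answered without lenses.

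**4. What off-lens scores could do.** If k of n scores are off-lens, counting all of them as not comfortable and then all as comfortable gives a range of width k/n, whichever subjects they came from. At n = 40, k = 5 gives 5/40 = 12.5 points and k = 10 gives 10/40 = 25 points.

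The position of the range depends on whose scores they are. Take an assumed 34/40 comfortable with k = 10:
- All ten from comfortable subjects: excluding them gives 24/30 = 80%, and the range is 24/40 = 60% to 34/40 = 85%.
- All six subjects who were not comfortable among the ten: excluding them gives 30/30 = 100%, and the range is 30/40 = 75% to 40/40 = 100%.
- In proportion: excluding them leaves about 85%.

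The direction of any bias is therefore not known in advance.

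**5. Missing scores.** Suppose all 8 extra subjects lack data (an outer bound) and 34 of the other 40 are comfortable. The range is 34/48 = 71% to (34 + 8)/48 = 42/48 = 88%.

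**6. Precision.** The exact (Clopper-Pearson) 95% limits for x of n are the 0.025 quantile of Beta(x, n − x + 1) and the 0.975 quantile of Beta(x + 1, n − x). The counts are illustrative, at n = 40:

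| Comfortable | Percent | Exact 95% CI |
|---|---|---|
| 28/40 | 70% | 53.5% to 83.4% |
| 34/40 | 85% | 70.2% to 94.3% |
| 38/40 | 95% | 83.1% to 99.4% |

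For scale, the smallest count whose lower limit exceeds 50% is 27/40, and the smallest whose lower limit exceeds 70% is 34/40. Neither reference value is in the plan.

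**The case against.** The best defence is that this is a pilot. The Introduction speaks of mapping comfort and Sample Size of a general understanding, so a descriptive percentage is a reasonable primary summary. That stands, and it is why rewording the aim as estimation would be enough. It does not remove the need for an interval or for a rule on which scores count.

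On the wear window, the Subjects text is a willingness criterion, while Visit 1, item 6 separately encourages 16 hours. A late starter who follows both would still have lenses in at the survey. That is fair, but encouragement does not assure it, and removal at 11:00 PM satisfies the criterion in Subjects.

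Three stronger readings are tempting and are not supported:
- **The endpoint cannot be computed for want of a cutoff.** The neutral anchor at 0 implies that comfortable means above 0. What is unstated is mainly how a score of exactly 0 is classed, worth 1/40 = 2.5 points per such score.
- **There are 49 competing primary results.** The text does not say that timepoint is crossed with day, seven of the 49 precede lens insertion, and Hypothesis 1 already singles out 16 hours. Publication Plans also makes comfort across the wear day the main outcome, apart from change over the month, though it names no day.
- **Off-lens scores will inflate the result.** That assumes they come from comfortable subjects. Step 4 shows that exclusion could move the figure either way.

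**Conclusion.** The point holds in a limited form. The plan promises to test comfort after 16 hours but provides only percentages, seven of them at 16 hours, with no interval and no day or summary named in advance. Its only tests address other questions. Separately, its own times allow a subject who meets the wear window in Subjects to give the 16-hour score after lens removal, for any start after 7:00 AM.

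Very high or very low results would be clear regardless. For results in between, the uncertainty matters: at n = 40 an observed 85% is compatible with 70.2% to 94.3%, and ten off-lens scores would add a 25-point counting range. The clock times and the count of seven follow from the documents. The comfortable counts, the share of late starters and the number of off-lens or missing scores are assumptions. The point should be fixed before the data are examined, but it does not invalidate the study.

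**What to change.** 1. **Wear times.** Reconcile the wear window in Subjects with the 16-hour survey and the wear-time encouragement in Visit 1, item 6. Which of them changes is for the investigators to decide.
2. **Off-lens and missing scores.** In Data Analysis, use the wear-hours data to report, for each survey day, how many subjects had lenses out before the 16-hour score. Do not count those scores as on-lens comfort, state how they and missing surveys enter the denominator, and show a best-case to worst-case range for both.
3. **The 16-hour result.** Name in advance one survey day, or one per-subject summary over the seven days, as the result for Hypothesis 1. Report it with an exact 95% CI and show all seven days beside it.
4. **The aim.** Reword the commitment to testing in the Specific Aim section as estimation, which fits the pilot purpose, or prespecify a reference proportion and justify it.
5. **Minor clarification.** Write down the cutoff that the neutral anchor implies (VAS > 0), and say how a score of 0 is classed.

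The cost is roughly a paragraph in Data Analysis, a sentence in Specific Aim, and a small edit to the wear text, which touches an eligibility criterion or subject instructions. No new visits or measurements are needed. The resulting 16-hour figure may be less favourable or less precise.
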